8.2. Primary Objective

The primary objective(s) of the study is to evaluate the impact of exposure to SC Peginterferon beta-1a or IM Interferon beta-1a before and during pregnancy on pregnancy outcome in female patients who had registered in the German PSP and of whom a pregnancy report and pregnancy outcome report is available.

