9.1.1. Primary Endpoints

- Number and proportion of
 - live births without congenital anomalies,
 - live births with congenital anomalies,
 - ectopic pregnancies,
 - spontaneous abortions,
 - elective abortions,
 - preterm births,
 - stillbirths

A spontaneous abortion is defined as fetal death before 22 weeks of gestation. A still birth is defined as fetal death at > 22 weeks gestation. A preterm birth is a birth before 37 completed weeks of gestation.

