9.2.1. Selection Criteria

The patients will only be included in the study if they meet all of the following criteria:

Inclusion Criteria

1. Female patients of at least 18 years at time of informed consent
2. Diagnosed RRMS or CIS (CIS indication only applicable for interferon beta-1a)

CONFIDENTIAL

The information contained herein may not be used, disclosed, or published without the written consent of
Biogen MA Inc.

3. Exposure to either SC Peginterferon beta-1a therapy or an IM Interferon beta-1a therapy before or during pregnancy
4. Registered in the PSP of the MSSC and agreed in writing to the privacy policy of the registration form
5. Reported pregnancy data (pregnancy report and pregnancy outcome report) available at MSSC. Note: only pregnancy data (i.e. obtained until 15 October 2021) will be considered.

For the prospective part of the study:

6. Ability to understand the purpose of the study and provide signed and dated study-specific informed consent form (ICF)
7. Pregnancy outcome in the retrospectively collected data was a live birth

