9.7. Data Analysis

This study is an observational study with focus on existing pregnancy reporting forms (retrospective part) and a patient's questionnaire which is completed at a single point of time (prospective part).

It will not be distinguished between the two treatments, i.e. the data will be pooled for analysis.

All documented data are analyzed by descriptive statistics, that is, no formal statistical hypothesis will be formulated, and no statistical tests will be carried out.

Categorical variables will be summarized descriptively by absolute frequencies and percentages. The denominator for all percentages will be the total number of pregnancies within the respective group, unless otherwise indicated. Percentages will be presented to one decimal place and will not be displayed for zero frequencies. A row denoted "Missing" will be included in all tabulations to clearly indicate the completeness of the collected data, i.e. missing data is included in the denominator of the percentages.

Continuous variables will be tabulated by descriptive statistics, i.e. the total number of pregnancies (n), number of pregnancies with missing values (Nmiss), mean, standard deviation, median, quartiles, minimum and maximum.

If sensible, free text entries will be transferred into appropriate encoding schemes to be analyzed in frequency tables. If appropriate, change of values during/after pregnancy to values before pregnancy will be calculated and analyzed using descriptive statistics or shift tables.

In case of missing or unknown data, no data imputation will be performed. For a complete presentation all obtained data will be listed.

A statistical analysis plan will be drafted and finalized before the end of the overall data collection to describe all analyses in more detail.

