9.7.2. Subgroup Analysis

Subgroup analyses will be performed with respect to patient's interferon beta-1a treatment history before during and after pregnancy. The primary endpoint will be evaluated in following subgroups:

- SC Peginterferon beta-1a or IM Interferon beta-1a was taken continuously before and during pregnancy
- SC Peginterferon beta-1a or IM Interferon beta-1a therapy was paused/stopped during pregnancy
- SC Peginterferon beta-1a or IM Interferon beta-1a therapy was started during pregnancy

The secondary endpoints will be evaluated in following subgroups:

- SC Peginterferon beta-1a or IM Interferon beta-1a was taken continuously before, during and after the pregnancy
- SC Peginterferon beta-1a or IM Interferon beta-1a therapy was started during pregnancy
- SC Peginterferon beta-1a or IM Interferon beta-1a therapy was paused during pregnancy and restarted promptly (within 1 week) after "life birth"
- SC Peginterferon beta-1a or IM Interferon beta-1a therapy was stopped during pregnancy and restarted more than a week after "life birth"
- SC Peginterferon beta-1a or IM Interferon beta-1a therapy was stopped during pregnancy and not restarted after "life birth"

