9.9. Limitations of the Research Methods

The study will be non-comparative. The lack of an internal reference therapy is a weakness of this study and should be kept in mind when interpreting the data. In non-interventional studies, the amount of data cleaning is limited. Therefore, missing values and/or implausible values are to be expected. The SAP will provide a detailed description on how to handle those values. In general, no substitution of missing values is planned.

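### The primary-endpoint subgroups in 9.7.2 depend on treatment behaviour after conception, which biases spontaneous abortion percentages across them, and women exposed only before pregnancy have no row

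*Protocol*

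**What the plan says.** Section 9.7.2 names three subgroups for the primary endpoint. The first holds pregnancies in which "SC Peginterferon beta-1a or IM Interferon beta-1a was taken continuously before and during pregnancy". The second is for women who interrupted or ended treatment, worded as "SC Peginterferon beta-1a or IM Interferon beta-1a therapy was paused/stopped during pregnancy". The third is for new starters, worded as "SC Peginterferon beta-1a or IM Interferon beta-1a therapy was started during pregnancy". The section gives no gestational window, no landmark, and no rule for a pregnancy that ends before a stop could have occurred.

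Three other passages bear on how these rows will read:

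- Section 9.1.1 makes spontaneous abortion a primary endpoint: "A spontaneous abortion is defined as fetal death before 22 weeks of gestation".
- Section 9.7 sets the denominator: "The denominator for all percentages will be the total number of pregnancies within the respective group, unless otherwise indicated".
- Section 9.2.1, criterion 3, admits "Exposure to either SC Peginterferon beta-1a therapy or an IM Interferon beta-1a therapy before or during pregnancy". A woman whose last dose was before conception is therefore eligible, but neither the primary nor the secondary list in 9.7.2 names a group for her.

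In the ENCePP checklist (Annex 2), exposure time windows (item 5.3) and information bias, including time-related bias (item 7.3), are marked not applicable. Item 12.1 ticks information bias as discussed in 9.9, but that section covers only the missing reference therapy and missing or implausible values.

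**The concern.** The subgroup label is not known at conception. It is settled by what happens later, in the same weeks in which spontaneous abortion occurs. A woman who would have stopped at week 8 but loses the pregnancy at week 6 never stops during pregnancy, so she is labelled continuous. Every pregnancy labelled stopped or started has, by definition, survived to the stop or start. This is immortal time. It acts on the percentages themselves, so the absence of significance tests does not remove it.

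The primary objective in 8.2 is to "evaluate the impact of exposure to SC Peginterferon beta-1a or IM Interferon beta-1a before and during pregnancy on pregnancy outcome", and rows set side by side by treatment history will be read as an answer to it. Section 7.1.1 names abortion as the risk seen in animal studies at extremely high doses, so a difference created by labelling would fall on a sensitive outcome.

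The second gap is one of classification. The objective includes exposure before pregnancy, but women with only that exposure are either left out of the subgroup tables or, on a loose reading of paused/stopped, mixed with women exposed in gestation.

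**Working it through.** **Plan's own figures.** Section 9.5 gives 202 + 245 = 447 pregnancies in 184 + 199 = 383 women, with 368 live births. Its one derived figure reproduces: 368 × 0.80 = 294, stated as about 290. No subgroup sizes or subgroup risks are planned, so there is nothing further to reproduce.

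**Inputs from the protocol.** N = 447 (9.5). Spontaneous abortion risk R = 10.7% (the European registry figure in 7.1.2). As a ceiling, all outcomes other than live birth: (447 − 368)/447 = 79/447 = 17.7%.

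**Assumptions not in the protocol.** c = share who never intend to stop; f = fraction of the planned stoppers' losses that come before the planned stop; a loss before the stop is labelled continuous. Every woman has the same risk R, so there is no drug effect. Pre-pregnancy-only women are set aside here.

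**Formulas.**

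- Continuous: R × [c + (1 − c)f] / [c + (1 − c)fR]
- Stopped: R × (1 − f) / (1 − fR)

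For any f > 0, c < 1 and R < 1, the first exceeds R and the second is below R. The direction therefore follows from the labelling rule alone.

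**Worked example**, c = 0.20, f = 1/3, R = 0.107:

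- Never intend to stop: 0.20 × 447 = 89.4 pregnancies, 9.6 losses.
- Planned stoppers: 357.6 pregnancies, 38.3 losses, of which 38.3/3 = 12.8 precede the stop and move to continuous.
- Continuous: (9.6 + 12.8)/(89.4 + 12.8) = 22.3/102.2 = 22%.
- Stopped: (38.3 − 12.8)/(357.6 − 12.8) = 25.5/344.8 = 7%.
- Ratio about 3.

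**Range.** The same no-effect model was run over 36 scenarios. Losses fell in weeks 4–21 with a weekly hazard declining at rate 0.1 or 0.2. Planned stops were at week 5, over weeks 5–8 or over weeks 6–12. The share never intending to stop was 5, 20 or 40%, and 0 or 20% had stopped before conception.

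| Overall risk | Continuous | Stopped | Ratio |
|---|---|---|---|
| 10.7% | 11.8–58.7% | 4.9–9.6% | 1.2–12 |
| 17.7% | 19.3–71.8% | 8.4–16.0% | 1.2–8.6 |

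Continuous holds between 14% and 74% of all spontaneous abortions. Its percentage is always inflated, but it does not always hold most of the events.

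**Grouping by status at conception.** The label is then fixed before any loss can occur. The same model returns R in every group, ratio 1.0.

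**The case against.** The strongest reply is that the main result is safe. The primary endpoints are pooled numbers and proportions in all eligible patients (9.1.1, 9.7.1.1), and relabelling cannot move them. Section 9.7 plans no tests, and 9.9 calls the study non-comparative. This stands, and it limits the point to the subgroup tables.

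A reader might infer that the study's internal reference group has been lost. The documents do not support that. Section 9.9 states openly that "The lack of an internal reference therapy is a weakness of this study", so none was planned. Women exposed only before pregnancy stay in the pooled set, their treatment history is extracted (9.4.1, Annex 3) and all data are to be listed. They are simply not shown separately. Their number is unknown, no look-back window is given, and they may differ in other ways, such as pregnancy planning.

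A reader might also infer that the table is bound to show a large excess under continued treatment. That goes too far. Stop times, loss times and intentions are not in the protocol, nor is the coding of a woman who stops on learning of the pregnancy or at the loss itself. At the low end the ratio is only about 1.2.

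Nor does the abortion bias extend to the secondary subgroups, because 9.7.1.2 restricts that set to live births. Only the missing pre-pregnancy row carries over.

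Finally, a coding rule could sit in the SAP. The group definitions, however, are fixed in the protocol, and a SAP that followed them would inherit the problem.

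**Conclusion.** The point holds for the subgroup tables. As written, 9.7.2 biases the spontaneous abortion percentage upward in the continuous group and downward in the paused/stopped group when the drug has no effect. The direction is certain once losses before a planned stop are labelled continuous and some such losses occur. The size is not determinable from the protocol: about 1.2-fold to 12-fold at an overall risk of 10.7%, entirely dependent on the assumed stop times, loss times and share intending to continue.

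Women exposed only before pregnancy are eligible but unclassified, or else mixed with women exposed in gestation. Section 7.1.2 describes exposure in the Nordic cohort as 86% before pregnancy and/or 31% in the first trimester, so such a group could be substantial. Its size here is unknown.

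This should be corrected before the SAP is finalised. It does not threaten the pooled primary analysis, so it is not a defect that must be fixed before the study can proceed.

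**What to change.** In 9.7.2:

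1. Tabulate pregnancy losses by exposure status at conception (exposed at conception versus last dose before conception), with pre-pregnancy-only exposure as its own descriptive row. Add the same row to the secondary subgroups.
2. Show continued, stopped and started only among pregnancies still ongoing at a stated gestational landmark, classified by status at that point and counting later outcomes. Otherwise, state that abortion percentages must not be compared across those groups.

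Neither change introduces a formal comparison. The costs are wording, programming and the following limits:

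- **Small row.** At 10.7%, the Wilson 95% interval is 2.5–27.8% for 22 pregnancies (2 events), 4.8–23.5% for 45 (5 events), 6.2–19.5% for 89 (10 events) and 6.3–16.8% for 134 (14 events).
- **Landmark drops early losses.** Assume loss times of week 5 plus an exponential lag of mean m weeks, truncated at week 22. The share lost before landmark L is [1 − exp(−(L − 5)/m)] / [1 − exp(−17/m)]. For m = 3 or 5 this is about 63% or 47% at week 8, and 91% or 78% at week 12. Of 447 × 0.107 = 48 losses, only about 4 to 11 would remain after week 12.
- **Data source.** Status at conception must be derived from the MSSC treatment history (9.4.1). The stop- and start-time endpoints in 9.1.2 belong to the secondary set, which covers only live births with a questionnaire.

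A time-varying exposure analysis is optional and depends on whether treatment dates exist for pregnancies that ended in loss.

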Research Question and Objectives:	
This study's main research question is to assess the course of pregnancy and infant outcomes in pregnant women with MS from Biogen's German MS Service-Center Database.
 
Primary Objective: The primary objective(s) of the study is to evaluate the impact of exposure to SC Peginterferon beta-1a or IM Interferon beta-1a before and during pregnancy on pregnancy outcome in female patients who had registered in the German PSP and of whom a pregnancy report and pregnancy outcome report is available.
 
Secondary Objectives: The secondary objectives of this study are applicable for a subpopulation of the above-mentioned population, i.e. for patients of whom data on a standardized questionnaire collected during a telephone interview is available. The secondary endpoints are as follows:
 
 • Average birth weight, average birth length, and head circumference of the newborn • To evaluate the impact of exposure to SC Peginterferon beta-1a or IM Interferon beta-1a before and during pregnancy on child development up to 48 months of age • To assess the SC Peginterferon beta-1a or IM Interferon beta-1a treatment behavior for pregnant women or women becoming pregnant in daily real life • To assess the other MS treatment behavior during/after pregnancy • To assess the use of certain concomitant medications (i.e. non-disease-modifying therapies) taken during pregnancy • To evaluate the effect of SC Peginterferon beta-1a or IM Interferon beta-1a exposure before, during, and after pregnancy on MS disease activity • To assess the effect of breastfeeding under SC Peginterferon beta-1a or IM Interferon beta-1a therapy on the MS disease activity • To assess the benefit of exclusive breastfeeding versus complementary feeding on the MS disease activity in women breastfeeding under SC Peginterferon beta-1a or IM Interferon beta-1a therapy

CONFIDENTIAL

The information contained herein may not be used, disclosed, or published without the written consent of Biogen MA Inc.

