9.1.2. Secondary Endpoints

- Average weight, average length, and average head circumference of the children from birth to 48 months
- Number and proportion of abnormalities diagnosed during pediatric check-ups under statutory programs in Germany and reported in the standardized German pediatric check-up booklet “Kinderuntersuchungsheft” (data on check-ups 1-8 will be collected covering the first 46 - 48 months of life). Refer to Annex 3 for recommended timepoints and details on the examinations.
- Number and proportion of women discontinuing SC Peginterferon beta-1a or IM Interferon beta-1a therapy during pregnancy and time to discontinuation in relation to beginning of pregnancy

CONFIDENTIAL

The information contained herein may not be used, disclosed, or published without the written consent of Biogen MA Inc.

- Number and proportion of women starting SC Peginterferon beta-1a or IM Interferon beta-1a therapy during pregnancy and time to start in relation to beginning of pregnancy
- Number and proportion of women restarting SC Peginterferon beta-1a or IM Interferon beta-1a therapy after birth and time to restart in relation to birth
- Number and proportion of women starting another MS therapy during/after pregnancy and time to start in relation to birth
- Number and proportion of women using other therapies during pregnancy (categorized by Paracetamol, other therapies for the alleviation of FLS), folic acid, medication for depression, corticosteroids, adrenocorticotrophic hormone, other therapies)
- Number and proportion of MS relapses in women with SC Peginterferon beta-1a or IM Interferon beta-1a therapy before, during and after pregnancy
- Change of EDSS during and after pregnancy to EDSS before pregnancy
- Lactation: number of women breastfeeding under SC Peginterferon beta-1a or IM Interferon beta-1a therapy and duration of SC Peginterferon beta-1a or IM Interferon beta-1a exposed breastfeeding
- Time to first MS relapse after introduction of the first supplemental feedings in women with SC Peginterferon beta-1a or IM Interferon beta-1a therapy during lactation

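### The child endpoints are grouped partly by treatment after birth, so some children exposed throughout pregnancy fall in no subgroup

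*Protocol*

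**What the plan says.** The child-development objective (Abstract, Secondary Objectives; repeated in Section 8.3) is to evaluate the impact of exposure "before and during pregnancy on child development up to 48 months of age". Treatment after birth is not part of it.

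Section 9.1.2 lists the child endpoints among the secondary endpoints: "Average weight, average length, and average head circumference of the children from birth to 48 months", together with abnormalities found at the statutory paediatric check-ups.

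Section 9.7.2 then states "The secondary endpoints will be evaluated in following subgroups", with no exception for the child endpoints. The five groups are:

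1. continuous: treatment "was taken continuously before, during and after the pregnancy";
2. "therapy was started during pregnancy", with no condition after birth;
3. "therapy was paused during pregnancy and restarted promptly (within 1 week) after" the live birth;
4. stopped in pregnancy, with restart later than one week after the live birth;
5. "therapy was stopped during pregnancy and not restarted after" the live birth.

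For the primary endpoint, the same section uses three classes defined by pregnancy alone: continuous before and during, paused or stopped during (one class), and started during.

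**The concern.** The grouping for the child endpoints should follow the exposure named in the objective. Four of the five groups carry a condition on what the mother did after delivery, and this has two consequences.

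First, the group that represents full prenatal exposure is restricted to children whose mothers stayed on treatment afterwards. Membership is then conditional on a decision made after the exposure of interest ended. In a safety study this is the exposure class of most interest.

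Second, groups 3, 4 and 5 have the same prenatal definition and differ only in whether and when treatment was restarted. Restart after delivery cannot alter weight, length or head circumference at birth, so for those endpoints the three-way split adds thin cells and no contrast in exposure.

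**Working it through.** **Size of the analysis set.** Section 9.5 gives 368 live-birth pregnancies and an 80% return rate: 0.80 × 368 = 294.4, consistent with the stated figure of about 290. This unit is pregnancies, not mothers. The Abstract gives about 310; the point does not depend on which is used.

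**Enumeration.** Four prenatal patterns were crossed with three post-birth patterns, and each combination was mapped to the two lists in Section 9.7.2. A restart within one week after continuous use was counted as continuous, which favours the plan.

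| Prenatal pattern | After birth: on treatment, or restart within 1 week | Restart after more than 1 week | Not on treatment | Primary-endpoint class |
|---|---|---|---|---|
| Before pregnancy only | none | none | none | none |
| Continuous before and during | group 1 | **none** | **none** | continuous |
| Paused or stopped during | group 3 | group 4 | group 5 | paused/stopped |
| Started during | group 2 | group 2 | group 2 | started |

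- Combinations with exposure in pregnancy: 3 × 3 = 9. The secondary list places 7 of 9; the primary list places 9 of 9.
- The two unplaced combinations both belong to the continuous class, where 2 of 3 post-birth patterns have no group.
- Groups 3, 4 and 5 all map to the single paused/stopped class of the primary list.
- The three combinations with exposure before pregnancy only are placed by neither list, although inclusion criterion 3 in Section 9.2.1 admits exposure before or during pregnancy.

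**Can the classes be recovered from the planned output?** The paused/stopped class can: Section 9.7 plans frequencies, n, mean and SD, so counts add and means and SDs can be pooled over groups 3 to 5 (medians and quartiles cannot). The continuous class cannot. Subtracting the five groups from the overall table leaves 12 − 7 = 5 combinations, which mix the unplaced fully exposed children (2 combinations) with children exposed only before pregnancy (3 combinations).

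**Illustration with assumed shares.** The protocol gives no subgroup shares, so these are ranges under assumption, not estimates.

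- Suppose 5% to 20% of 290 pregnancies were exposed throughout and, in 10% to 50% of those, treatment did not continue after birth. The number in no subgroup runs from 290 × 0.05 × 0.10 = 1.45 to 290 × 0.20 × 0.50 = 29, that is, about 1 to 29.
- Suppose 50% to 90% of 290 are paused or stopped (145 to 261). Take the birth-weight SD of 606.4 g quoted in Section 7.1.2 for the exposed Nordic cohort. The 95% half-width for mean birth weight is 1.96 × 606.4/√145 = 98.7 g down to 1.96 × 606.4/√261 = 73.6 g for the merged class. For each of three equal parts it is 1.96 × 606.4/√(145/3) = 171.0 g down to 1.96 × 606.4/√(261/3) = 127.4 g.

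**The case against.** Several points on the other side stand.

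- **The grouping still carries prenatal information.** A reader might infer that child development is split by behaviour after birth instead of by exposure in pregnancy. The text does not support that: group 1, group 2 and groups 3 to 5 are three different prenatal patterns, and group 2 has no condition after birth.
- **The objective is not made unanswerable.** Coarse contrasts between continuous, started and paused or stopped exposure are planned, and groups 3 to 5 can largely be recombined.
- **No child is lost from the study.** Unplaced children stay in the secondary analysis set (Section 9.7.1.2) and its overall summaries, and Section 9.7 provides for listing all data.
- **The gap may be narrow.** Section 9.7.2 sets no minimum duration of treatment after pregnancy. A woman who continued for some weeks and then stopped can be read into group 1. The gap is clear only for a stop at delivery or a resumption after an interval.
- **Treatment after birth could matter for later growth.** Growth and check-ups run to 48 months, and breastfeeding under interferon is itself a secondary endpoint. This limits the argument about the three-way split to birth size in the strict sense. It does not remove the mismatch: the objective names only exposure before and during pregnancy, and Section 7.1.2 regards levels in milk as negligible, though on limited data.
- **Pooling early and late stops is not a defect of this list.** The primary list does the same, and finer timing is detail that a SAP commonly supplies.

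The SAP could add classes, but a SAP that follows the protocol inherits this list. No other section gives a prenatal split for the child endpoints, and the checklist in Annex 2 (item 5.3) marks exposure time windows as not applicable.

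**Conclusion.** The point holds in a limited form. For the child endpoints, Section 9.7.2 fixes a grouping that does not match the objective. It leaves some fully exposed children without a subgroup, so the continuous group is selected on a post-birth decision, and it divides one prenatal class into three. This follows from the wording alone: 7 of 9 in-pregnancy combinations are placed, against 9 of 9 under the classes that the section already uses for the primary endpoint.

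The number of children affected cannot be computed from the protocol; the range of about 1 to 29 rests wholly on assumed shares. The study is descriptive with no tests, so no inference is invalidated. It remains worth correcting because the rule is stated, bears on the most exposed children, and cannot be undone from the planned summary tables.

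**What to change.** In Section 9.7.2, separate the two uses of the list.

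- Keep the five groups for maternal disease-activity, treatment-restart and lactation endpoints, which they suit.
- For birth size, growth and check-up abnormalities, use the three primary-endpoint classes (continuous before and during; paused or stopped during; started during), whatever happened after birth.
- Add a fourth class for exposure before pregnancy only, which is eligible but in neither list.
- Within the paused/stopped class, show the time of stopping descriptively. The protocol already plans to report discontinuation of "therapy during pregnancy and time to discontinuation in relation to beginning of pregnancy", so no new data are needed.

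The cost is a few lines of text and one extra grouping variable derived from treatment data already due for extraction (Section 9.4.1). The downside is that some cells, such as continuous or started in pregnancy, may be small.

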8.3. Secondary Objectives

The secondary objectives of this study are applicable for a subpopulation of the above-mentioned population, i.e. for patients of whom data on a standardized questionnaire collected during a telephone interview is available. The secondary endpoints are as follows:

- To evaluate the impact of exposure to SC Peginterferon beta-1a or IM Interferon beta-1a before and during pregnancy on **child development** up to 48 months of age
- To assess the SC Peginterferon beta-1a or IM Interferon beta-1a **treatment behavior** for pregnant women or women becoming pregnant in daily real life
- To assess the other MS **treatment behavior** during/after pregnancy

CONFIDENTIAL

The information contained herein may not be used, disclosed, or published without the written consent of
Biogen MA Inc.

- To assess the use of certain concomitant medications (i.e. non-disease-modifying therapies) taken during pregnancy
- To evaluate the effect of SC Peginterferon beta-1a or IM Interferon beta-1a exposure before, during, and after pregnancy on MS **disease activity**
- To assess the effect of breastfeeding under SC Peginterferon beta-1a or IM Interferon beta-1a therapy on the MS disease activity
- To assess the benefit of exclusive breastfeeding versus complementary feeding on the MS disease activity in women breastfeeding under SC Peginterferon beta-1a or IM Interferon beta-1a therapy

CONFIDENTIAL

The information contained herein may not be used, disclosed, or published without the written consent of Biogen MA Inc.

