9.4.2. Prospective Data Capture

If the pregnancy report or the pregnancy outcome report is incomplete, i.e. the data above was not collected, the open questions will be addressed during a telephone interview performed by the MSSC and the new information will be entered into the MSSC database. No further assessments other than completion of the questionnaire are applicable for patients participating in the prospective study part. The patient questionnaire is completed at a single point of time during the telephone interview performed by the MSSC.

The patient questionnaire covers the following questions:

- Abnormalities diagnosed during pediatric check-ups under statutory programs as reported in the standardized German pediatric check-up booklet “Kinderuntersuchungsheft” (data on check-ups 1-8 will be collected covering the first 46-48 months of life)
- Pregnancy and family anamnesis
- Vitamin K prophylaxis
- Body weight, height, head circumference of the child as documented for check-ups 2-8.
- Lactation:
 - Exclusive breastfeeding and duration (1st week, 1 month, 2 months, 3 months, 5 months, 6 months, 7-9 months, 10-12 months, > 12 months) of breastfeeding
 - Supplemental feedings (starting month after birth)
- Other MS therapies (non-interferon beta-1a DMTs) during or after pregnancy and start relative to birth (during pregnancy, < 1 week after birth, after 1 week, after 2 weeks, after 3 weeks, after 4 weeks, after 6 weeks, after 2 months, after 3 months, after 4 months, after 5 months, after 6 months, after 7 months, after 8 months, after 9 months, after 10 months, after 1 months, after 12 months or later))
- Frequency of MS relapses in the year before pregnancy
- Time (1st trimester, 2nd trimester, 3rd trimester) and frequency of MS relapses during pregnancy

CONFIDENTIAL

The information contained herein may not be used, disclosed, or published without the written consent of Biogen MA Inc.

- Time (< 1st month, 1st – 2nd month, 3rd - 4th month, 5th - 6th month, 7th - 8th month, 9th - 10th month, 11th - 12th month, 13th - 14th month, 15th - 16th month, 17th - 18th month, > 18th months) and frequency of MS relapses after pregnancy/birth
- EDSS before, during and after pregnancy

The information collected by the MSSC will be stored in a secure database.

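### Section 9.7.2 defines the post-birth subgroups by interferon history alone, so disease activity in women who did not restart mixes untreated women with women on another MS therapy, and one treatment course has no subgroup

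*Protocol*

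**What the plan says.** Protocol Section 9.7.2 states the basis of the subgroups: "Subgroup analyses will be performed with respect to patient's interferon beta-1a treatment history before during and after pregnancy". For the later outcomes it says "The secondary endpoints will be evaluated in following subgroups" and lists five:

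1. interferon taken throughout, including after birth;
2. interferon started in pregnancy;
3. interferon paused and resumed within a week of birth;
4. "therapy was stopped during pregnancy and restarted more than a week after" birth;
5. "therapy was stopped during pregnancy and not restarted after" birth.

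No other MS therapy enters any of these definitions, and the fourth has no upper limit on the time to restart.

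Section 8.3 includes the objective to evaluate the effect of "exposure before, during, and after pregnancy on MS disease activity". Section 8.1 also asks whether disease progression differs by interferon exposure.

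Switching is foreseen. Section 9.1.2 has the endpoint "Number and proportion of women starting another MS therapy during/after pregnancy and time to start in relation to birth", and Section 9.4.2 collects the start of other MS therapies relative to birth. Section 9.4.2 also collects the time "and frequency of MS relapses after pregnancy/birth", in bands.

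**The concern.** The fifth subgroup is the only one defined by no interferon after birth, so a reader will look there for disease activity off interferon. It holds two different kinds of women: those on no MS therapy, and those who moved to another one. Their relapses and EDSS changes would be shown as one figure. If the other drug works, the figure looks better than that of untreated women. If women switched because their disease was active, it may look worse.

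Women who continued through pregnancy and then stopped or switched after birth belong to none of the five subgroups. Their post-birth disease activity drops out of the subgroup tables.

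Membership of the restart subgroups is also fixed by what a woman did later. A relapse in the months before a late restart, possibly the reason for it, sits in the row labelled as restarted unless the table separates it.

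**Working it through.** **Analysis set.** Section 9.5 gives 368 live-birth pregnancies and an 80% return rate: 0.80 × 368 = 294.4, which agrees with the stated figure of about 290 questionnaires. This total is spread over the five subgroups. The protocol gives no share of women who restarted, did not restart or switched, so subgroup sizes cannot be derived.

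**Definitions tested against possible courses.**

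| Course | Subgroup under 9.7.2 |
|---|---|
| Stopped in pregnancy, no MS therapy after birth | Fifth (not restarted) |
| Stopped in pregnancy, other MS therapy after birth | Fifth (not restarted) |
| Stopped in pregnancy, relapse after birth, interferon restarted later | Fourth (late restart), including the relapse before restart |
| Continued through pregnancy, stopped or switched after birth | None |

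The first two rows cannot be told apart, and the last has no place. Both results follow from the text without any assumed number.

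**Whether the data can separate them.** Section 9.4.1 extracts interferon use before, during and after pregnancy, and time to restart is an endpoint in Section 9.1.2. Section 9.4.2 records the start of other MS therapies in bands of weeks to months, but lists no stop. Post-birth relapses come in 11 bands, mostly two months wide up to month 18 and open-ended afterwards. The split by other MS therapy is therefore available. The order of relapse and restart or switch is available between bands, but not within one.

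**Direction only.** All rates here are assumptions, chosen to show the sign and not the size. Set the untreated relapse rate to 1 and the rate on interferon to 0.70. If a share s of the not-restarted group takes another drug with relative rate r:

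- group rate = (1 − s) + s × r
- apparent interferon ratio = 0.70 / group rate

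Results for s from 10% to 70%:

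- r = 0.5: group rate 0.95 to 0.65, apparent ratio 0.74 to 1.08.
- r = 1.5 (switched because of active disease): group rate 1.05 to 1.35, apparent ratio 0.67 to 0.52.

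The distortion can go either way.

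For a restart at month m of a 12-month window, under the same assumed rates:

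- share of relapses before restart = m / (m + 0.70 × (12 − m))
- m = 3: 3 / 9.3 = 32%
- m = 6: 6 / 10.2 = 59%
- m = 9: 9 / 11.1 = 81%

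Without an upper limit on the time to restart, the late-restart row can describe mostly untreated time.

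**The case against.** **Switching is not ignored.** A reader might infer that the plan overlooks it. The documents do not support that. Starting another MS therapy is a secondary endpoint, and the secondary endpoints are evaluated in the subgroups. The number and timing of switchers should therefore appear within the not-restarted group, and a reader will see how mixed it is. This stands. A count of switchers still does not separate their relapses and EDSS from those of untreated women.

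**No counting rule is stated.** A reader might also infer that relapses will be credited to the wrong treatment. The protocol nowhere assigns a relapse to a treatment, Section 9.7 leaves detail to a SAP that is not at hand, and the time bands allow display by period. This stands too. What can be said is only that relapses before a late restart fall under the restarted label unless they are shown separately. The subgroup definitions, by contrast, are already fixed in Section 9.7.2.

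**The study is descriptive.** Section 9.7 plans no tests, and Section 9.9 calls the study non-comparative. No passage calls the not-restarted group an untreated control, and confounding by disease activity would remain after any split. So the harm is a table that cannot be interpreted, not a wrong test. Sections 8.1 and 8.3 nevertheless ask for disease activity by exposure, and Section 9.9 mentions neither switching nor treatment timing.

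**Limits on repair.** Crediting every event to the treatment then in use would need stop dates for other MS drugs, which Section 9.4.2 does not list. Asking for the month of each relapse would change a questionnaire that needs ethics approval (Section 10.1), and would rely on recall possibly years later, for doubtful gain. Both points stand, and neither measure is proposed.

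**Conclusion.** The point holds as a defect of definition. For relapses and EDSS after birth, the not-restarted subgroup pools women on no MS therapy with women on another one, and women who continued through pregnancy and then stopped or switched have no subgroup. As they stand, these descriptive tables cannot inform the objective on interferon exposure after pregnancy and disease activity. Relapses before a late restart will also appear under the restarted label unless separated.

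The conclusion rests on the wording of Section 9.7.2, not on assumed rates. Its size is unknown because the protocol gives no frequencies of restart or switch; the illustrative ratios show only that the direction is open. A SAP may already add the split. If so, Section 9.7.2 should be brought into line with it.

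**What to change.** In Section 9.7.2, for the disease-activity endpoints:

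- Split the not-restarted subgroup into women on no MS therapy and women who started another MS therapy.
- Add a subgroup for women who continued interferon through pregnancy and then stopped or switched after birth.
- As far as the collected time bands allow, report post-birth relapses before the first restart or switch separately from later ones, and state that the order within a band is unknown.

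This uses items already listed in Sections 9.4.1 and 9.4.2 and needs no new question, so the work is a text change and programming. The downside is smaller cells: about 290 questionnaires would be spread over seven subgroups instead of five (5 + 1 from the split + 1 added). That is acceptable in descriptive tables, provided the counts are shown.
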